4.5 Safety Population

The safety population consists of all patients who are randomized and received any dose (including a partial dose) of the study medication (PRX-102 or agalsidase beta). Assignment is by actual treatment received. The full set of measurements available will be used for the safety analysis All safety analyses will be performed on this population.

5. TREATMENT DESCRIPTIONS

Unless otherwise indicated, in the summary tables, the treatments will be identified by PRX-102 and agalsidase beta.

6. IMPACT OF COVID-19

The impact of COVID-19 on the study was assessed in August 2020 and then revisited as part of the interim analysis Blinded Data Review Meetings (BDRM) in March 2021. As the pandemic is still ongoing, it will be revisited at the BDRM prior to the final analysis and documented in the meeting minutes.

As of March 2021, the impact of COVID-19 is considered to be minimal, as detailed in the list below.

In light of that, for the interim analysis, the Sponsor did not see the need to account for the effect of the pandemic in the primary and safety analyses. Several tables and listings were added (see Section 8.1) in order to be able and discuss the impact and support the choice of no changes on the primary and safety analyses.

Generally speaking, even before the start of the pandemic, the protocol allowed for a mixture of home care and site visits. Home care includes infusion of study drug, blood sampling for the majority of the laboratory tests including primary endpoint and biomarkers, monitoring of Adverse Events (AE), medications and vital signs. Other procedures, including imaging, stress test, echocardiogram and questionnaires are carried out only on site. This use of home care was expanded with no need for protocol amendments and the logistics for this implementation were already in place.

- As of the cut-off date for the interim analysis, no patients have been diagnosed with COVID-19. There were no deaths and no early termination due the pandemic.
- Enrolment for the study was completed in Oct 2019 and hence there is no impact on enrolment.
- The use of home infusions was increased due to COVID-19 restrictions, so there is no or very minimal impact on compliance to study drug.
- Drop out from study was low prior to the pandemic. As of the cut-off date for the interim analysis, one patient has dropped out since the outbreak of the pandemic, but for reasons not related to the pandemic.
- There should be no or very little impact on the primary end-point, since blood samples for serum creatinine are continued to be taken at home (see Section 8.1).
- The protocol allowed for a window of ±3 days in the drug administration visit. The majority of the visits remained within these limits. This is assessed and documented as part of the Blinded Data Review Meeting Report.
- Procedures which must be taken on site may be postponed until the patient can reach the site. Although all efforts were done to perform them even with a delay, in some cases they were cancelled or were conducted as part of the extension study (PB-102-F60) and will be considered missing for the purpose of the analysis of this study. This is assessed and documented as part of the Blinded Data Review Meeting Report.
- For several patients the study was prolonged:
 - o For patients who reach Week 104 (visit 53; end of study) and could not perform the end of study visit on site, as planned, the study was extended with the home-care procedures (as detailed above). The patients perform the other procedures of visit 53 when a site visit is possible. In some instances, when the patient performed the delayed visit 53 on site, procedures which required additional coordination of site staff (cardiac MRI, stress test, brain MRI and echocardiogram) were postponed further and performed after the patient switched to the open label extension study PB-102-F60, thus it was decided that those assessments will be excluded from the end of study visit of PB-102-F20 if they performed more than 2 months after the date of Visit 53. This is documented as part of the Blinded Data Review Meeting Report.
 - O Some patients were able to perform Week 104 (visit 53) on site, at the planned time, but were not able to switch to the extension study (since the rollover requires site visit), and they continued to be treated at their home with the same drug of study PB-102-F20 until it was possible to have a site visit for the extension study. This is documented as part of the Blinded Data Review Meeting Report.
- The timeline of the interim analysis or its objective are not changed due to COVID-19.

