6 INVESTIGATIONAL PLAN

6.1 Overall Study Design and Plan – Description

The study will be a randomized, double blind, active-control study of the efficacy and safety of PRX-102 compared to agalsidase beta in adult Fabry disease patients with impaired renal function under treatment already with agalsidase beta for at least a year. Patient age will be 18 to 60 years. The estimated glomerular filtration rate (eGFR) using the CKD-EPI equation will be 40 to 120 mL/min/1.73 m² and evidence of renal disease progression of at least 2 mL/min/1.73 m²/year.

Patients will receive intravenous infusions of PRX-102 1 mg/kg or agalsidase beta 1 mg/kg every two weeks. Infusion duration will initially be 3 hours, but may be decreased gradually after establishment of tolerability by agreement of the investigator and Protalix Medical Director.

Efficacy will be determined by the slope of eGFR over the course of the study. Two analyses of efficacy will be performed – at 12 and 24 months of treatment. For regulatory purposes, demonstration of non-inferiority of PRX-102 compared to agalsidase beta at 12 months for submission of MAA to the European Medicines Agency and superiority at 24 months for FDA BLA submission will be considered trial success.

At the end of the study patients may be offered to continue to an extension open label study; patients on the agalsidase beta arm will be offered to move to PRX-102 1 mg/kg every 2 weeks.

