3. STUDY DESIGN

The study is a randomized, double blind, active-control study of the efficacy and safety of PRX-102 compared to agalsidase beta in adult Fabry disease patients with impaired renal function under treatment with agalsidase beta for at least one year and on a stable dose for at least 6 months. Patient age will be 18 to 60 years. The estimated glomerular filtration rate (eGFR) at screening using the Chronic Kidney Disease Epidemiology Collaboration (CKD-EPI) equation will be between 40 to 120 mL/min/1.73 m² and evidence of renal disease progression of at least - 2 mL/min/1.73 m²/year will be present. No more than 50% of the patients enrolled will be female.

Patients will be randomized to receive intravenous infusions of PRX-102 1 mg/kg or agalsidase beta 1 mg/kg every two weeks at a 2:1 ratio. Randomization will be stratified by urine protein to creatinine ratio (UPCR) of <1 or ≥ 1 gr/gr by spot urine sample. Infusion duration will initially be 3 hours but may be decreased gradually after establishment of tolerability by agreement of the investigator and Protalix Medical Director.

The primary efficacy endpoint is the mean annualized change (slope) of eGFR over the course of the study as estimated from a longitudinal mixed model. The comparison of the slopes between the two arms will be evaluated after the last patient complete at least 12 months of treatment (interim analysis) and when the last patient complete 24 months of treatment (final analysis). The objective of the interim analysis is to demonstrate non-inferiority with a margin of -3.0 mL/min/1.73 m²/year and will be used to support the submission of a MAA to the EMA. The objective of the final analysis with the data from 24 months of treatment is to demonstrate superiority and will be part of the confirmatory trial supporting the BLA conversion from Accelerated Approval to traditional approval.

At the end of the study all patients may be offered the opportunity to continue to an open-label extension study (PB-102-F60) with PRX-102 1 mg/kg administered every 2 weeks.

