10.4 Cardiac Assessments

10.4.1 Cardiac MRI

Left ventricular mass (LVM), left ventricular mass index (LVMI, indexed to patient's body surface area (g/m²)), and left ventricular ejection fraction (%EF) will be summarized using descriptive statistics for each visit that includes these evaluations. The change from baseline will be summarized. A 95% CI for the difference between the two in the change from baseline to Week 52 and to Week 104 arms will be presented using t-distribution for 2-samples. The LVM and LVMI analysis will be done separately for patients who have hypertrophy at baseline, patients who don't have this abnormality, and patients whose hypertrophy at baseline is missing. Hypertrophy is defined as LVMI above 91 g/m² for males and LVMI above 77 g/m² for female (Kawel-Boehm (2015)).

In case that LVM at a visit is available, and LVMi is missing, the following rule will be used to calculate LVMi:

$$LVMI = LVM / BSA.$$

Du Bois and Du Bois (1916) will be used to calculate the BSA:

BSA =
$$0.007184 \times W^{0.425} \times H^{0.725}$$
,

where H is the height (cm) measured at screening and W is the weight (kg) measured at the same visit of the cardiac MRI. In case that weight at the visit is missing, the last available weight prior to the visit will be used. This is the formula which is used by the vendor that provides the cardiac MRI assessments.

The analysis will be repeated by gender and by FD classification.

A shift from baseline to Week 52 and to Week 104 in the number of left ventricular fibrosis segments (based on cardiac MRI) will be presented in a shift table by treatment group.

A shift from baseline to Week 52 and to Week 104 in the number of patients who have Hypertrophy at Baseline (Yes / No / Missing) will be presented by treatment group and by treatment group and gender.

For definition of baseline for cardiac MRI, see Section 7.3. For the same reasons discussed in Section 7.3, delays of up to 60 days in the performance of cardiac MRI at Week 52 or Week 104 will be considered with planned visit.

Not all patients can perform cardiac MRI (e.g., patients with pacemaker), and for others only part of the assessments can be done (e.g., patients who cannot receive contrast dye to avoid the contrast nephrotoxicity). This information will be included in the listing.

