For some patients, cardiac MRI at Week 104 was postponed due to COVID-19 and eventually performed as part of the extension study, so the data will not be analyzed as part of this study (Section 6).

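### The SAP has two incompatible rules for Week 104 imaging and stress tests done after roll-over to PB-102-F60, and one would analyse assessments made on open-label PRX-102 as control-arm data

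*SAP*

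**What the plan says.** SAP Section 6 deals with on-site procedures delayed by COVID-19 in two places.

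- A general bullet says that some delayed procedures "were conducted as part of the extension study (PB-102-F60) and will be considered missing for the purpose of the analysis of this study". It sets no time limit.
- A later sub-bullet concerns patients whose end-of-study visit was delayed. It notes that cardiac MRI, stress test, brain MRI and echocardiogram were in some instances "postponed further and performed after the patient switched to the open label extension study PB-102-F60", and that these are to be "excluded from the end of study visit of PB-102-F20 if they performed more than 2 months after the date of Visit 53".

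The endpoint sections add the following.

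- Section 10.4.1 (cardiac MRI): "delays of up to 60 days in the performance of cardiac MRI at Week 52 or Week 104 will be considered with planned visit". Its last paragraph says that for some patients the Week 104 scan was "eventually performed as part of the extension study, so the data will not be analyzed as part of this study", and it refers to Section 6.
- Section 10.4.2 (echocardiogram) says the same about tests done in the extension, with the same reference.
- Section 10.7 (stress test) says only that Week 104 data may be missing for a few patients, again citing Section 6.
- Section 7.1 says that data beyond Visit 53 are listed and may enter an analysis, to be settled analysis by analysis, but are left out of by-visit summary tables.

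On treatment, SAP Section 3 says that all patients may "continue to an open-label extension study (PB-102-F60) with PRX-102 1 mg/kg administered every 2 weeks". Protocol Section 6.1 agrees: "patients on the agalsidase beta arm will be offered to move to PRX-102". SAP Sections 4.3 and 10 analyse secondary efficacy endpoints on the ITT set, by randomized arm.

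**The concern.** A cut-off of 2 months that applies only to assessments made after the switch has a purpose only if those made sooner are kept. The general bullet and the closing statements of Sections 10.4.1 and 10.4.2 keep none of them. Two programmers working from this SAP could therefore build different Week 104 data sets for cardiac MRI and echocardiogram, and for the stress test if they weigh the two parts of Section 6 differently.

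The choice matters because the extension is not a continuation of randomized treatment for the control arm. A PRX-102 patient who rolls over stays on the same enzyme. An agalsidase beta patient changes enzyme. If that patient's post-switch scan is kept, it enters the comparison as a control value although it was taken after PRX-102 had been started. LVMI by MRI is a named secondary endpoint (SAP Section 2.2.2), and the cardiac MRI measures have a between-arm 95% confidence interval at Week 104.

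**Working it through.** The plan gives no figure on this point to reproduce. The check compares the rules and then bounds the exposure.

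**1. How each rule treats a cardiac MRI done 40 days after Visit 53, after roll-over**

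| Source in SAP | Treatment of the scan |
|---|---|
| Section 6, general bullet | Missing |
| Section 6, sub-bullet | Not excluded (40 days is under 2 months) |
| Section 10.4.1, 60-day window | Counts as Week 104; no condition on current treatment |
| Section 10.4.1, closing paragraph | Not analysed |
| Section 7.1 | May be analysed, but not in by-visit tables |

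For an echocardiogram, the sub-bullet conflicts with the general bullet and with Section 10.4.2. For a stress test, the conflict lies wholly within Section 6, because Section 10.7 adds no rule. Brain MRI is only listed (Section 11.9), so no estimate depends on it.

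**2. Open-label exposure before a retained assessment**

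Inputs: infusions every 14 days (SAP Section 3); a window of 2 months (59 to 62 days) or 60 days. Assumption: the first PB-102-F60 infusion is 14 days after Visit 53.

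- Infusion days after Visit 53: 14, 28, 42, 56. All four fall within 59 to 62 days.
- Fifth infusion: 5 × 14 = day 70, or day 67 if given 3 days early (the visit window of this study, assumed to carry over). Both are outside the window.
- A retained post-Visit 53 assessment therefore follows 0 to 4 open-label infusions.
- Share of the treatment period: 60 / (104 × 7) = 60 / 728 = 8.2%.

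**3. Share of the control arm**

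The documents do not give the number affected. Assumed range: 1 to 5 control patients. Denominators from SAP Section 3.1: about 22 planned completers and about 26 randomized.

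- Of 22: 1/22 = 4.5%; 5/22 = 22.7%.
- Of 26: 1/26 = 3.8%; 5/26 = 19.2%.

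Section 10.4.1 analyses LVM and LVMI separately by baseline hypertrophy, so one patient weighs more within a stratum. Stratum sizes are not given.

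**4. Outputs affected**

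- Between-arm intervals for change to Week 104: LVM, LVMI and ejection fraction (Section 10.4.1).
- Descriptive tables: fibrosis-segment and hypertrophy shifts (10.4.1), echocardiogram shifts (10.4.2), stress test counts and shift (10.7).
- Not affected: the primary eGFR slope analysis (9.2).

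**The case against.** The best defence is that the text can be reconciled. The sub-bullet names four procedures in a defined situation, and a specific rule normally qualifies a general one. Sections 10.4.1 and 10.4.2 describe only some patients and point back to Section 6, so they could be read as applying the 2-month rule. Section 6 also records that the choice was decided and documented in the Blinded Data Review Meeting Report, and says that COVID-19 impact will be revisited before the final analysis. Accepting slightly late scans to limit missing data is a legitimate trade-off.

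Part of this stands. No sentence says outright that post-switch assessments are kept; that is an inference from the exclusion condition. A reader might take the 60-day MRI window as a second rule that deliberately admits them. It is not: it applies equally to Week 52, when nobody has rolled over, and it rests on the scheduling and repeat-scan reasons in Section 7.3. Its weakness is only that it does not require the patient still to be on randomized drug.

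The defence does not remove the point. The general bullet and the endpoint sections carry no time limit, and a reference to a section that holds both rules settles nothing. If the specific rule does prevail, the treatment misattribution is confirmed: early post-switch control assessments are then analysed as control.

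A reader might also infer that keeping these scans flatters a non-inferiority result. The documents do not support that. Non-inferiority is defined only for the eGFR analyses (Sections 9.2 and 9.3), and Section 7.6.2 rules out significance claims for other efficacy endpoints.

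**Conclusion.** The inconsistency is real, and it lies in the current SAP text. Under the reading that retains assessments within 2 months, a former agalsidase beta patient assessed after about 0 to 4 open-label PRX-102 infusions would be analysed as control. If the enzymes differ on these measures, this may attenuate the between-arm difference in LVM, LVMI and ejection fraction at Week 104. The echocardiogram, fibrosis, hypertrophy and stress test tables would also carry misattributed values.

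The size cannot be computed. The number of affected control patients is not stated; 1 to 5 of 22 planned completers (4.5% to 23%) is an assumed range. The infusion count assumes a first extension dose 14 days after Visit 53. The documents offer no evidence that so short an exposure changes these measures detectably, so the bias may be small. With the primary analysis unaffected and no significance claims on these endpoints, this is a minor point that is worth correcting because correction is cheap.

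**What to change.** Before database lock, state one rule in SAP Section 6 and apply it in Sections 10.4.1, 10.4.2 and 10.7. A delayed Week 104 assessment counts only if it is within 60 days of Visit 53 **and** before the first PB-102-F60 infusion. Otherwise it is missing for this study and is only listed. Use 60 days throughout instead of mixing it with 2 months.

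Report the number of affected assessments by arm and procedure, separating those excluded for lateness from those excluded because the extension infusion had started.

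This rule still keeps in-window assessments from patients who continued their randomized drug at home while waiting for a site visit. The cost is a change of SAP wording and a few Week 104 assessments that may become missing, in either arm.

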7. STATISTICAL ISSUES

7.1 Statistical Methods

Descriptive statistics, namely number of patients (n), mean and its standard error (SE), standard deviation (SD), median, minimum and maximum for continuous variables, and counts and percentages for categorical variables, will be provided. For some variables, the 25th and 75th percentile will be presented.

Statistical comparison of the efficacy endpoints between treatments of PRX-102 and agalsidase beta will be described in detail in relevant sections of this document.

Unless otherwise specified, summaries by visit will present only scheduled visits based on the protocol planned visits for each procedure. Procedures which were performed in an unscheduled visit or in scheduled visits in which the procedure was not planned per protocol, will only be listed. Data collected in premature withdrawal visit will be listed but not tabulated.

Listings will show data collected on all enrolled subjects (including screening failures), when applicable. In listings: patients will be sorted to show treated patients first (PRX-102 followed by agalsidase beta) and then patients who were screening failures. Visits (scheduled and unscheduled) within subject will be shown chronologically based on the date of the visit.

Due to the COVID-19 pandemic, the study may be prolonged beyond Week 104 (visit 53 data collected beyond visit 53 will be listed and may be included in the analysis (discussed for each analysis, as relevant). These data will not be presented in summary tables by visit.

7.2 Missing Data

Imputation of missing data associated with AE severity and relatedness are described in Section 11.2.

Several imputation strategies will be used to impute missing data as part of a sensitivity analysis supporting the primary analyses (see Section 9.4).

Below are imputation rules related to missing or incomplete dates of medication or Acute Kidney Injury AE.

7.2.1 Partial or Missing Dates of Medication

The following imputations will be used in case of incomplete dates of agalsidase-beta treatment required for the calculation of its duration prior to the study:

- The middle of the month (i.e., 15th) will be used if only the day is missing.
- In case the year is not missing, but the month is missing, the month will be imputed to July. If the day is missing as well then it will be imputed to the 1st of July
- No imputation will be done in case the year is missing.

No imputation will be done in case of fully missing medication date.

In some of the analyses, a flag of whether a medication was used at a certain visit is needed (e.g., use of Angiotensin-Converting Enzyme Inhibitor (ACEi) or Angiotensin Receptor Blocker (ARB) treatment at baseline or usage of pain medication at baseline or in the last visit). In case that partial start date and/or end date exist, imputation will be based on the above rules and determination of the flag will be based on the imputed dates and comparison with the date of the visit of interest.

In case that the year is missing from the start date, the determination of usage of a medication at different visits will be based on the stop date of the medication. If the year of the stop date is missing, then the determination will be based on the "Ongoing" status of the medication form as follows: if the ongoing status is Yes then it is assumed that the medication was taken throughout the study (including at baseline and last visits), and if the ongoing status is No then it is assumed the medication was stopped prior to the baseline visit.

Since information on infusion premedication is collected at both the medication form and the drug administration form then determination of usage of infusion premedication at a given visit is based on a different algorithm described in Section 11.8.2.

7.2.2 Partial or Missing Dates of Episodes of Acute Kidney Injury

Episodes of Acute Kidney Injury (AKI) are reported by the investigators as an AE. An AKI episode is defined between the start and the end date of the AKI AE. The following rules will be followed in the case of an incomplete start or end date of an AKI event:

AKI start date

- If month and year are available and day is missing, the 1st of the month will be imputed. In case the event is during the month of the first infusion, it will be imputed to the date of 1st infusion.
- If month is missing and year is available then if the year is the same as the year of 1st infusion date, then should be the date of 1st infusion. Otherwise, the date should be set to January 1st.
- If year is missing then the date should be imputed to date of 1st infusion.

AKI end date

- If month and year are available and day is missing, the last day of the month will be imputed. In case the event is during the month of the last infusion, it will be imputed to the date of end of study.
- If month is missing and year is available then if the year is the same as the year of last infusion the date should be the last day in the study. Otherwise, the date should be set to December 31st.
- If year is missing then the date should be imputed to last day in the study.

Serum creatinine samples taken for the study while the AKI AE was still considered as on-going will be excluded from the eGFR slope calculation and summary tables and considered to be missing. See Section 9.1 for more details.

